#### Definition of MTD, MAD, and RP2D

The estimated MTD is the dose level associated with approximately 30% of DLT-evaluable subjects experiencing a DLT. The target interval for the DLT rate is 25%-35%. Due to the discreteness of the dose levels and in the interest of the safety of subjects, the estimated MTD is the highest tested dose level with DLT rate  $\leq 35\%$  in at least 6-12 DLT-evaluable subjects. In general, the MTD will equal the RP2D unless one or more of the following suggest that an alternate dose below the MTD would be preferable:

- Clinically significant anti-tumor effect.
- The MTD is not achieved, in which case the MAD may become the RP2D.
- The occurrence of late and relevant AEs that occur after the DLT period.
- Cumulative toxicity of the MTD or MAD, reflecting that the administration of multiple cycles at the MTD or MAD is not feasible.
- AEs observed beyond Cycle 1 that would require setting the RP2D below the MTD level.

The SRC will evaluate the totality of the events and consider whether they could result from a cumulative toxicity or are significant for the determination of the RP2D.

The MAD is declared without an MTD based on a dose level with an observed DLT rate <25% (the lower bound of the MTD range) and where sufficient safety and efficacy signals have been observed.

The RP2D is the dose chosen for further study based on Phase 1 study results. The RP2D will take into account late and relevant toxicities that occur after the DLT period and/or the cumulative tolerance of multiple cycles of treatment. If the MTD or MAD proves to be clinically feasible for long-term administration in a reasonable number of subjects, then this dose usually becomes the RP2D. Further experience with the MTD/MAD may result in a RP2D dose lower than the MTD/MAD (eg, if in the expansion part >25% of subjects require a dose reduction due to toxicity, then the sponsor may convene an SRC to determine if a lower RP2D needs to be determined).

#### **4.1.2. Part 2A Tumor-Specific Dose Expansion Administration**

Following determination of the MTD/MAD in Part 1 Dose Escalation, separate tumor-specific cohorts of 15 subjects will be treated with KZR-261 using the identified MTD/MAD or SRC recommended dose. Following an interim analysis of the first 15 subjects in each cohort, the SRC will decide whether to enroll an additional 20 subjects into the respective tumor-specific cohort for a total of 35 enrolled subjects per tumor-specific cohort.

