3. STUDY DESIGN

3.1. Overview of Study Design

This FIH, open-label, multicenter, Phase 1 study is designed to assess the safety and tolerability, preliminary anti-tumor activity, and the PK characteristics of KZR-261, as well as identify the RP2D. KZR-261 will be administered as a 30- to 60-minute IV infusion via a central line on Days 1, 8, and 15 of a 4-week (28-day) treatment cycle. (Doses may be held up to 7 days for resolution of non-DLT toxicity.) Eligible subjects will have locally advanced or metastatic solid malignancies and no approved therapies, or refused such therapies if available.

The study will be conducted in 2 parts: Part 1 (Dose Escalation) and Part 2 (Part 2A –Dose Expansion and Part 2B – Dose Optimization).

[figure not shown]
In Part 1, increasing doses of KZR-261 will be administered in an “i3+3” design to approximately 70 subjects to evaluate the safety and tolerability, PK, and pharmacodynamics of KZR-261, including identifying the MTD or MAD.

The Dose Expansion phase will commence following determination of the MTD/MAD and a review of the totality of safety data from Part 1. Part 2A will further characterize the safety profile of KZR-261 at the MTD or MAD and evaluate the anti-tumor activity of KZR-261 in subjects who have select malignancies. Up to 175 subjects may be enrolled in up to 4 tumor-specific cohorts (such as malignant melanoma [including uveal melanoma], mesothelioma, mCRPC, and mCRC) and 1 “All-Tumors” cohort. Additional or different tumor-specific cohorts may be investigated at the Sponsor’s discretion. Each tumor-specific cohort will enroll 15 subjects during Stage 1, expanding up to 35 subjects (Stage 2) as defined by a prespecified futility analysis and if the tumor type is not selected for investigation in Part 2B (see below). If futility is not rejected after Stage 1 (ie, prespecified criteria for futility are met), subsequent enrollment to that Part 2A cohort will cease. The All-Tumors cohort may enroll up to 35 biopsy-evaluable subjects.

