3.5. Safety Review Committee (Parts 1, 2A, and 2B)

The SRC will consist of the Medical Monitor (or designate), other Kezar representative(s), and participating Investigators. All Investigators who enroll subjects in the cohort under review will be consulted prior to the SRC meeting if they are unable to attend the scheduled meeting.

During Part 1, the committee will review safety data from the current cohort and previous cohorts before deciding on escalation to the next dose level. Dose escalation may occur only after the SRC has agreed ([Section 3.2.1.1](#)).

The totality of safety data from Part 1 will be reviewed prior to a declaration of the MTD/MAD. Available PK data may also be reviewed.

During Parts 2A and 2B, the SRC will periodically monitor safety data through the end of the study.

In Part 2, the study will be halted if there is one Grade 5 or two Grade 4 AEs in different subjects that are considered at least possibly related to KZR-261. Exceptions to the halting criteria include asymptomatic Grade 4 laboratory abnormalities (eg, neutropenia) that resolve either with or without routine supportive care measures and without sequelae. If this scenario occurs, a formal safety analysis will be conducted, and the findings will be submitted to the IND for the FDA to review prior to enrolling additional subjects.

A separate SRC Charter will describe the responsibilities of this committee for both dose escalation and dose expansion/dose optimization.

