10.6. Interim Analyses

The Go/No-Go futility analysis for each tumor-specific cohort in Part 2A will be based on CBR as the primary outcome measurement (as defined in [Section 10.5.5](#)) after Stage 1 enrollment of 15 subjects. Each of the expansion cohorts is based on the following assumptions:

- Each expansion cohort has a maximum sample size of 35 with one interim futility analysis at 15 subjects. At the interim analysis, if there is 1 or no subject with CBR (ie, CBR rate <7%), further enrollment into the cohort will be stopped for futility. If futility is rejected at the interim analysis (ie, 2 or more of 15 subjects with clinical benefit), the final analysis will be based on a total 35 subjects (ie, 20 additional subjects evaluable for CBR). Note: Outcomes (ie, presence or absence of clinical benefit) for subjects enrolled in Part 1 with the same tumor type and who received the same dose of KZR-261 as evaluated in the corresponding Part 2A, tumor-specific cohort may be included among the initial 15 subjects at the interim analysis, as described above.

The operating characteristics of this design are presented in [Table 13](#). If the true CBR is less than 5%, there is a reasonable chance to reach the futility criterion at interim. On the other hand, if the true CBR is 20% or higher, the probability to stop for futility is moderately low (<20%).

Table 13: Operating Characteristics of Dose Expansion Phase (Part 2A)

True CBR	Interim Analysis (N=15)		Final Analysis (N=35)		
	Pr(Futility*)	Pr(obs. CBR ≥15% 6 or more subjects with CBR)	Pr(obs. CBR ≥20% 7 or more subjects with CBR)	Pr(obs. CBR ≥25% 9 or more subjects with CBR)	Pr(obs. CBR ≥25% 9 or more subjects with CBR)
5%	83%	<1%	<1%	<1%	<1%
10%	55%	11%	5%	<1%	<1%
15%	32%	39%	25%	7%	7%
20%	17%	67%	54%	25%	25%
25%	8%	86%	78%	52%	52%
30%	4%	95%	92%	76%	76%
35%	1%	98%	97%	91%	91%

CBR=clinical benefit rate; obs.=observed; Pr=probability

* 1 or fewer subjects with CBR among the first 15 subjects.

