- At the interim analysis, if there is 1 or no subject with clinical benefit (ie, CBR rate <7%), further enrollment into the cohort will be stopped for futility. If futility is rejected at the interim analysis (ie, 2 or more of 15 subjects with clinical benefit), the final analysis will be based on a total 35. Note: Outcomes (ie, presence or absence of clinical benefit) for subjects enrolled in Part 1 with the same tumor type and who received the same dose of KZR-261 as evaluated in the corresponding Part 2A, tumor-specific cohort may be included among the initial 15 subjects at the interim analysis, as described above.

The operating characteristics of this design are presented in [Table 3](#). If the true CBR is less than 5%, there is an 83% probability to reach the futility criterion at interim. On the other hand, if the true CBR is 20% or higher, the probability to stop for futility is 17%.

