**Table 3: Operating Characteristics of Dose Expansion Phase (Part 2A)**

True CBR	Interim Analysis (N=15)		Final Analysis (N=35)		
	Pr(Futility*)	Pr(obs. CBR ≥15% 6 or more subjects with CBR)	Pr(obs. CBR ≥20% 7 or more subjects with CBR)	Pr(obs. CBR ≥25% 9 or more subjects with CBR)	
5%	83%	<1%	<1%	<1%	
10%	55%	11%	5%	<1%	
15%	32%	39%	25%	7%	
20%	17%	67%	54%	25%	
25%	8%	86%	78%	52%	
30%	4%	95%	92%	76%	
35%	1%	98%	97%	91%	

CBR=clinical benefit rate; obs.=observed; Pr=probability

\* 1 or fewer subjects with CBR among the first 15 subjects.

In Part 2B (Dose Optimization), up to 120 subjects may be enrolled into up to 4 tumor-specific cohorts (30 per each tumor-specific cohort [15 per dose level]) based on the totality of data after data from Parts 1 and 2A has been assessed. The sample size for Part 2B is based on clinical considerations.

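### SAP 4.1.2 leaves the Stage 2 decision to the SRC without citing the 0–1 of 15 futility stop in Protocol 10.6 and SAP 5; Table 3 holds only if that stop is binding and every passing cohort goes to 35

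*SAP*

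**What the plan says.** Most of the plan fixes the Stage 1 decision by a count.

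- Protocol 10.6: "if there is 1 or no subject with CBR (ie, CBR rate <7%), further enrollment into the cohort will be stopped for futility".
- SAP 5: "if there is 1 or no subject with clinical benefit (ie, CBR rate <7%), further enrollment into the cohort will be stopped for futility".
- Protocol 3.1: if the futility criteria are met, "subsequent enrollment to that Part 2A cohort will cease". SAP 3.1 says the same.
- The footnote to the futility column of SAP Table 3 uses the same event: "1 or fewer subjects with CBR among the first 15 subjects".

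SAP 4.1.2 describes the step differently. Following the interim analysis of the first 15 subjects, "the SRC will decide whether to enroll an additional 20 subjects into the respective tumor-specific cohort". It states no count and does not point to SAP 5.

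Protocol 3.5 describes the SRC's work in Part 2 as safety review: "During Parts 2A and 2B, the SRC will periodically monitor safety data through the end of the study". Protocol 8.1.1 lists safety triggers for SRC review. Neither section gives the committee a futility decision. Protocol 3.5 refers to a separate SRC Charter, which is not among the documents.

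SAP 18 gives a third version. It sets the target at CBR of at least 6.7% (1/15) and the lower reference at below 6.7%.

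**The concern.** The Stage 1 interim is the one pre-specified efficacy gate in Part 2A. A mandatory stop at 0 or 1 of 15 and an open committee decision are different rules, and the SAP contains text for both. If SAP 4.1.2 were followed literally, a cohort that met the futility criterion could still receive 20 more subjects. The published stopping probabilities would then not describe what happens.

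Precedence does not clearly settle it. SAP 1 says that the SAP's statistical methods supersede those of the protocol, so a reader cannot simply fall back on Protocol 10.6, and the SAP itself is not uniform. A cohort with exactly 1 of 15 is stopped under SAP 5, reads as a go under SAP 18, and is left to the SRC under SAP 4.1.2.

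**Working it through.** **Inputs.** Stage 1 n = 15 and maximum N = 35, so 20 are added (Protocol 10.6: "Each expansion cohort has a maximum sample size of 35 with one interim futility analysis at 15 subjects"). Stop at 1 or fewer of 15. True CBR p from 5% to 35% (Table 3). Final thresholds of 6, 7 and 9 of 35.

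**Step 1: reproduce the table.** Let X1 ~ Bin(15, p) and X2 ~ Bin(20, p), independent.

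- Pr(futility) = P(X1 = 0) + P(X1 = 1)
- Pr(r or more of 35) = Σ over x = 2 to 15 of P(X1 = x) · P(X2 ≥ r − x)

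At p = 5%, Pr(futility) = 0.4633 + 0.3658 = 0.829, against 83% in the table.

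| True CBR | Pr(futility) | ≥6/35 | ≥7/35 | ≥9/35 | Table 3 |
|---|---|---|---|---|---|
| 10% | 54.9% | 11.5% | 5.1% | 0.6% | 55 / 11 / 5 / <1 |
| 20% | 16.7% | 67.2% | 53.8% | 25.0% | 17 / 67 / 54 / 25 |

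All 28 cells (7 rows by 4 columns) reproduce. Two alternatives do not fit. A single stage of 35 gives 72.8% for 6 or more at CBR 20%. A stop only at 0 of 15 gives Pr(futility) of 46% at CBR 5% and 3.5% at CBR 20%. The table therefore describes the binding stop at 1 or fewer, with every passing cohort taken to 35.

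**Step 2: let the SRC override the stop.** The documents give no SRC criterion, so assume an override probability w between 0 and 1 and no other departure.

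- Pr(stop) = (1 − w) · Pr(futility). At CBR 5% this is 83% (w = 0), 41% (w = 0.5) or 0 (w = 1).
- The gain in Pr(6 or more of 35) is w · [P(X1 = 0) · P(X2 ≥ 6) + P(X1 = 1) · P(X2 ≥ 5)].

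With w = 1:

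- CBR 10%: 0.2059 × 0.0113 + 0.3432 × 0.0432 = 0.0171, so 11.5% becomes 13.2%.
- CBR 20%: 0.0352 × 0.1958 + 0.1319 × 0.3704 = 0.0558, so 67.2% becomes 72.8%.
- The higher thresholds move less. At CBR 20%, 7 or more goes from 53.8% to 56.7%, and 9 or more from 25.0% to 25.5%.

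**Step 3: exposure.** Each overridden cohort adds 35 − 15 = 20 subjects. Over four cohorts the ceiling is 80.

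**Step 4: discretion in the other direction.** Suppose instead that a passing cohort is stopped with assumed probability q. At CBR 20%, Pr(stop) = 0.167 + 0.833q, which is 25%, 38% or 58% for q = 0.10, 0.25 or 0.50. Pr(7 or more of 35) = (1 − q) × 53.8%, which is 48%, 40% or 27%.

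**Step 5: how often the disputed count occurs.** P(X1 = 1) is 37% at CBR 5% and 34% at CBR 10%. SAP 5 and SAP 18 thus disagree on a common result.

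**The case against.** SAP 4.1.2 is a dose-administration section, and it places the SRC's decision after the interim analysis, whose rule is in SAP 5. It can be read as naming who acts on the count rather than replacing it. SAP 3.1, in the same document, keeps the mandatory stop. SAP 1 gives the SAP precedence on statistical analysis methods, and who opens Stage 2 is arguably not one. For the same reason, SAP 19's statement that no protocol analyses were changed proves little. The SRC Charter may bind the committee to the count. All of this stands, but SAP 4.1.2 does not say it.

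Two stronger readings are tempting and are not supported.

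- A reader might infer that Table 3 is not the operating characteristics of the plan as written. It is exactly right for the rule in Protocol 10.6 and SAP 5, the sections that define the interim and present the table.
- A reader might infer that SRC discretion is what makes the final CBR come from outcome-selected cohorts. Any futility stop selects on outcome, and overriding it reduces that selection. Discretion to end a passing cohort also does not originate in SAP 4.1.2: Protocol 3.3 makes the increase to 35 permissive, and Protocol 3.1 lets the sponsor close a Part 2A cohort and move the tumor type to Part 2B. Step 4 therefore describes a limit that the table already has.

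The ceiling of 80 is also remote. It needs all four cohorts to meet futility (0.829⁴ = 47% even if every true CBR is 5%) and all four to be overridden, and those subjects lie within the planned maximum of 175.

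**Conclusion.** The concern holds as a conflict of wording at the Stage 1 gate. SAP 4.1.2 gives the SRC an unqualified decision, the protocol and the rest of the SAP (apart from SAP 18's boundary) require a stop at 0 or 1 of 15, and the protocol sections on the SRC describe only a safety role in Part 2. The table is correct for the count rule and conditional on two assumptions that it does not state: a binding stop, and full enrollment of every passing cohort.

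If overrides were allowed, the main effects would be on the stopping probability, for which the tabled value becomes an upper limit, and on exposure, at 20 subjects per overridden cohort. The effect on the final columns is small: under 6 percentage points at every tabled CBR, even if every stop is ignored. These sizes rest on independent binomial outcomes and on the assumed range for w, because the documents give no SRC criterion. The Charter could narrow the issue.

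**What to change.** 1. In SAP 4.1.2, state that Stage 2 opens only if at least 2 of the first 15 subjects have clinical benefit (SAP 5) and the tumor type is not selected for Part 2B. Limit the SRC's role at this point to safety review as in Protocol 3.5 and 8.1.1.
2. In SAP 18, replace the 6.7% (1/15) boundary with the SAP 5 count. Changing 4.1.2 alone would leave two boundaries in the SAP.
3. Under Table 3, note that the figures assume a binding stop and enrollment of every passing cohort to 35.
4. Check that the SRC Charter agrees.

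If the sponsor wants a non-binding rule, Protocol 10.6 should say so, and columns computed without the stop should be added to the table.

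The binding version costs a few sentences in the SAP and no recalculation. The sponsor gives up only continuation past futility, which the protocol already rules out. The non-binding version needs a protocol amendment and the extra columns.

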## **5. SAMPLE SIZE AND POWER CONSIDERATIONS**

The sample size for Part 1 will be approximately 70 subjects, but the actual sample size will depend on the number of dose levels of KZR-261, number of subjects per dose level, and the number of subjects treated at the MTD or the MAD(s) of KZR-261.

Dose escalation will continue accruing until one of the three stopping conditions below is triggered:

- The maximum sample size has been achieved,
- MTD/MAD has been identified with sufficient accuracy: data from 6 to approximately 12 subjects have been accumulated at a dose that is deemed to be the MTD/MAD, or
- All doses explored appear to be overly toxic and the MTD cannot be determined.

Due to binomial data variability in small samples, DLTs may be observed in a first cohort(s) by chance even when the true probability (DLT) is fairly low. This could result in the estimated posterior DLT rate exceeding the targeted 30% very early in the trial, triggering an early stop when very few subjects (2-4) have been treated. To prevent stopping the trial prematurely in such cases, a step-down option with a lower dose of 0.9 mg/m^2 is added to the dose grid. This dose

will be explored only if a high DLT rate occurs in the first cohort assigned to 1.8 mg/m^2, ie, it will not be used as a starting dose.

Upon identification of the MTD/MAD at the conclusion of Part 1, the study will continue with up to 4 tumor-specific expansion cohorts and 1 All-Tumors cohort in Part 2A. As previously noted, the tumor-specific cohorts (n = 15 at interim) may be increased up to 35 subjects per cohort to more precisely estimate the anti-tumor activity of KZR-261, if there is a sufficient efficacy signal at the interim analyses ([Protocol Section 10.6](#)) and if the tumor type is not selected for investigation in Part 2B (dose optimization). The All-Tumors cohort may enroll up to 35 biopsy-evaluable subjects.

Go/No-Go futility analysis for each tumor-specific cohort in Part 2A will be based on CBR as the primary outcome measurement (as defined in [Protocol Section 10.5.5](#)) after Stage 1 enrollment of 15 subjects. Each of the expansion cohorts is based on the following assumptions:

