## 13. EFFICACY ANALYSES

All efficacy analyses will be performed on the Response Evaluable Population.

All efficacy data will be listed and summarized with descriptive statistics.

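### The Part 2A Go/No-Go rule has no single denominator: with 14 or fewer evaluable subjects, exactly one benefit means stop by the count and continue by the rate

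*SAP*

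**What the plan says.** **Size.** The interim comes "after Stage 1 enrollment of 15 subjects" (SAP 5; Protocol 10.6 has the same basis). SAP 4.1.2 then has the SRC decide on 20 more, "for a total of 35 enrolled subjects per tumor-specific cohort". Protocol 10.6 describes that stage differently: "the final analysis will be based on a total 35 subjects (ie, 20 additional subjects evaluable for CBR". SAP 5 gives the total of 35 without mentioning evaluability. No section calls the first 15 evaluable for CBR, although a total built from 15 plus 20 evaluable subjects implies it.

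**Who is counted.** SAP 13 states: "All efficacy analyses will be performed on the Response Evaluable Population". SAP 6.2 admits to that population only subjects with a response assessment both at baseline and afterwards. Protocol 10.5.8 keeps subjects who discontinue in every analysis, and allows imputation only where the SAP specifies it. SAP 13.2 assigns a best response of NE to a subject lost before any assessment, yet SAP 6.2 would leave that subject out.

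**The rule.** Protocol 10.6 stops a cohort "if there is 1 or no subject with CBR (ie, CBR rate <7"%), and SAP 5 stops it "if there is 1 or no subject with clinical benefit (ie, CBR rate <7"%). The cohort continues with "2 or more of 15 subjects with clinical benefit". SAP 18 gives a rate only: at least 6.7% (1/15) is the target value, and anything below it the lower reference value.

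**Stated performance.** SAP 5 says that "if the true CBR is 20% or higher, the probability to stop for futility is 17"%. Protocol 10.6 says below 20% for the same case. Protocol Table 13 and SAP Table 3 give 83% at a true CBR of 5%.

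**The concern.** A count and a rate are interchangeable only when the denominator is fixed, and here it is not. A Stage 1 subject with no post-baseline assessment is foreseeable: the first scheduled on-treatment imaging is at the end of Cycle 2 (Protocol 7.2.10), the disease is advanced and pretreated, and exclusion criterion 23 itself anticipates illness that prevents the first response assessment. The replacement rules cover Part 1 only. Neither document says whether such a subject is one of the 15.

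At stake is whether each of up to four cohorts stops or takes on 20 more subjects. The same Stage 1 data could give either answer, and the operating characteristics may describe a rule other than the one applied.

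**Working it through.** **Inputs.** Stage sizes 15 and 20, stop at 0 or 1, rate gloss below 7% (Protocol 10.6, SAP 5); printed probabilities (Protocol Table 13, SAP Table 3). The documents give no evaluable fraction for Part 2A, so 1 to 3 non-evaluable subjects of 15 are examined as an assumption.

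**1. Reproduce the table.** With n subjects and true CBR p, the chance of stopping by count is

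Pr(X ≤ 1) = (1 − p)^n + n·p·(1 − p)^(n−1).

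At n = 15 and p = 0.20: 0.8^15 + 15 × 0.2 × 0.8^14 = 0.035 + 0.132 = 16.7% (printed 17%). For true CBR of 5, 10, 15, 20, 25, 30 and 35% the results are 82.9, 54.9, 31.9, 16.7, 8.0, 3.5 and 1.4% (printed 83, 55, 32, 17, 8, 4 and 1%).

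For the final columns, sum over x ≥ 2 of Pr(X1 = x; 15) × Pr(X2 ≥ r − x; 20). At p = 0.20 and r = 6, 7, 9 this gives 67.2, 53.8 and 25.0% (printed 67, 54 and 25%). So the table rests on exactly 15 + 20 subjects in the denominator.

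**2. Compare count and rate.** 1/15 = 6.67% is below 7%, so both say stop. 1/14 = 7.14%, 1/13 = 7.69% and 1/12 = 8.33% are not, so the count says stop and the rate says continue. With 0 benefits both stop; with 2 or more both continue.

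**3. Chance of the split with 14 evaluable.** Pr(X = 1) = 14·p·(1 − p)^13. At p = 0.10: 1.4 × 0.9^13 = 35.6%. At p = 0.20: 2.8 × 0.8^13 = 15.4%.

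**4. Futility probability under each reading.** With 14 or fewer, the rate stops only at 0 benefits, so its probability is (1 − p)^n.

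| Evaluable of 15 | Count, CBR 5% | Count, CBR 20% | Rate, CBR 5% | Rate, CBR 20% |
|---|---|---|---|---|
| 15 | 82.9% | 16.7% | 82.9% | 16.7% |
| 14 | 84.7% | 19.8% | 48.8% | 4.4% |
| 13 | 86.5% | 23.4% | 51.3% | 5.5% |
| 12 | 88.2% | 27.5% | 54.0% | 6.9% |

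**5. SAP 18.** Taken as written, 1 of 15 meets the target value, so it reads as go even with all 15 evaluable. SAP 5 makes the same result a stop.

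**The case against.** The best defense is that the operative rule is a count on a fixed 15. Stop and go are both written as counts, the table footnote repeats the count among the first 15, and the rate is only a gloss on 1/15. If Protocol 10.5.8 governs and an unassessed subject counts as no benefit, the denominator stays 15 and the split never occurs. That reading is reasonable but not secured. Protocol 10.5.8 does not say how an unassessed subject is scored, SAP 13 points the other way, and the SAP introduction gives the SAP's methods precedence while SAP 19 declares no changes from the protocol.

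Three further points stand:

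- A reader might infer that the final-stage probabilities also fall sharply. They do so only if the thresholds 6 and 7 are held while the denominator shrinks. The columns are also labeled by observed rate. With 30 evaluable (13 + 17) at true CBR 20%, at least 15% (5 of 30) has probability 65% against the printed 67%, and at least 20% (6 of 30) has 52% against 54%. No final success rule is tied to these counts.
- Defining 15 and 35 as CBR-evaluable would equally make the table correct, but it needs enrollment to continue until those numbers are reached. The choice between the two is a judgment.
- Counting treated subjects does not restore power for CBR among evaluable subjects. A CBR of 20% among evaluable subjects with 13 of 15 evaluable is 0.20 × 13/15 = 17.3% among treated subjects. At n = 15 the futility stop is then about 24%, close to the 23.4% above.

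**Conclusion.** The denominator of the Go/No-Go rule is inconsistent across the documents and should be settled. The size depends on the reading and on an assumed evaluable fraction. By the count, the SAP's 17% at true CBR 20% is missed with one non-evaluable subject (19.8%), and the protocol's limit of 20% with two (23.4%). By the rate with 14 evaluable, the chance of stopping a cohort with true CBR 5% drops from 83% to 49%.

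A reader might infer that any non-evaluable subject reverses the decision or voids the stated properties. The documents do not support that. The decision splits only with 14 or fewer in the denominator and exactly one benefit, and the protocol's limit of 20% survives one non-evaluable subject. Nor is it shown that the trial would drop unassessed subjects at the interim; the documents leave that open. The conflict in SAP 18 needs no evaluability assumption.

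**What to change.** - **Protocol 10.6 and SAP 4.1.2, 5 and 18:** base the interim on the first 15 treated subjects and the final analysis on 35 treated subjects. Count a treated subject with no qualifying assessment as having no clinical benefit.
- **Protocol 10.6 and SAP 5:** delete the parenthetical rate of under 7%, so that the rule is the count alone: 0 or 1 stops, 2 or more continues.
- **Protocol 10.6:** describe the added 20 as treated subjects rather than as evaluable for CBR.
- **SAP 18:** replace the 6.7% (1/15) wording with the same count.
- **SAP 6.2 and 13:** state that the Go/No-Go CBR and the final Part 2A CBR use treated subjects, with the Response Evaluable result as supportive.
- **Protocol Table 13 and SAP Table 3:** state that the true CBR is the rate among treated subjects. The printed probabilities then apply to that rate, and a given CBR among evaluable subjects corresponds to a lower treated rate.

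The cost is wording, plus a slightly lower reported CBR because unassessed subjects stay in the denominator. No enrollment is added.
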